Version 3.0	20-June-2022	
1. The sections for date were removed from the title page.2. Medline Industries, Inc. was changed to Medline Industries, LP throughout the document.3. The inclusion and exclusion criteria were modified in the synopsis and the main body of the protocol.4. The dressings' change frequency was changed from twice weekly to at least once weekly.5. The study duration was changed from 6-12 months to 6-60 months.6. The "Investigator Acknowledgement Signature" page was modified to correctly include the abbreviations and remove the term "device".7. The "Schedule of Activities" table was modified to include the changes in the study design.8. The reference numbers of all the clinical products used in this study were included.9. Product descriptions such as instructions for use and labeling information, and product images were removed from the appendix of the protocol.10. The objectives and endpoints table in the protocol was modified so that the objectives and endpoints in the table are similar or identical

		
to the objectives and endpoints stated in the synopsis.
 
11. The “Study Procedures and Assessments” section was modified per our current protocol template and changes in the study design.12. The “Severity of Adverse Event” section was modified per our current protocol template.13. The “Expectedness”, “Adverse Event Reporting”, and “Serious Adverse Event Reporting” sections were modified per our current protocol template.14. An interim analysis was added in the “Statistical Considerations” section.15. All the case report forms were removed from the appendix of the protocol.16. Minor changes were made in the protocol regarding naming conventions, abbreviations, and wording used in our current protocol template.
Version 4.0	30-June-2022	
1. One of the inclusion criteria was modified in the synopsis and the main body of the protocol.

1. PROTOCOL SUMMARY

1.1. Synopsis

Title: A comparative evaluation of a marine polysaccharide dressing and a carboxymethylcellulose dressing on subjects with lower extremity venous ulcers.

Study Description: Venous leg ulcers are lower extremity ulcers that develop due to sustained venous hypertension resulting from chronic venous insufficiency. Varicose veins, deep vein thrombosis, poor calf muscle function, arterio-venous fistulae, obesity, and history of leg fracture are some of the risk factors for venous ulceration. Numerous dressing types exist to treat these ulcers. This study will compare a marine polysaccharide (MPS) dressing (Opticell® Ag⁺ dressing manufactured by Medline Industries, LP, referred to as MPS-Ag) to a carboxymethylcellulose (CMC) dressing (Aquacel® Ag Advantage dressing manufactured by ConvaTec, referred to as CMC-Ag), and will determine which dressing better manages these wounds with regard to wound size and periwound skin condition. Subjects will be randomized to receive either MPS-Ag dressing or CMC-Ag dressing.

Objectives: **Primary objective:** Evaluate and compare wound size changes in subjects when either MPS-Ag dressing or CMC-Ag dressing is used.

Secondary objectives: Compare (1) periwound skin condition, (2) subject perception of pain during dressing changes, and (3) dressing shrinkage.

Endpoints: **Primary endpoint:** Changes in wound size in subjects when MPS-Ag dressing or CMC-Ag dressing is used.

Secondary endpoints: (1) Evaluation of peri-ulcer skin assessment scale (PUSAS) score weekly for entire duration of study, (2) Subjective evaluation of subject pain perception during dressing changes using a numerical pain scale, and (3) Change in surface area of the dressing.

Study Population: Sixty-eight adult subjects with lower extremity venous ulcers will be selected.

Inclusion criteria will be:

- Males and females, 18 years or older.

- Subject is able and willing to comply with requirements of this trial protocol
- Subjects must be able to communicate effectively with study personnel
- Subject has lower extremity venous ulcer wound, as determined by the site Principal Investigator (PI).
- Subject has adequate lower extremity arterial circulation as determined by the site PI at the time of enrollment.
- Size of subject's wound is between 1cm² and 100cm².
- Duration of subject's wound is <52 weeks.

Exclusion criteria will be:

- Subjects who are pregnant, nursing, or planning to become pregnant during the course of the study.
- Subjects who have known allergies to any ingredient(s) in the clinical products used in this study including silver.
- Subjects who do not wish to use product(s) derived from shellfish.
- Subjects with substance use disorder within the past six months.
- Subjects with active infection and/or currently receiving antibiotic treatment for the wound included in the study.
- Subjects who are currently enrolled in another research study which includes investigational treatment and/or medication.
- Subjects judged by the site PI or sub-investigator to be inappropriate as a subject of this study.
- Subject has previous or current systemic disease(s) which, in the judgement of the site PI, is likely to interfere with the study. However, subjects with well-controlled diabetes mellitus (DM) (HbA1c < 8.5) shall be permitted.
- Subjects who receive any additional product or procedure/activity that could influence wound healing, such as chemical debridement, use of other wound cleansers, additional hydrogel or alginate wound products etc.

Phase: Phase IV, Post-Market

Description of Sites/Facilities Multiple wound care centers

Enrolling Participants:

Description of Study Intervention: Subjects who meet all of the inclusion criteria and none of the exclusion criteria will be randomized to receive either MPS-Ag dressing or CMC-Ag dressing. The wound will be cleansed with Skintegrity® wound cleanser, followed by application of MPS-Ag dressing or CMC-Ag dressing. Compression bandage (CoFlex® TLC Two Layer Compression Bandage system) will be applied over the dressing. The dressings will be changed at least once weekly but can be changed earlier by the clinician depending on the level of exudate. Wound assessments will be carried out weekly. The performance of both the dressings will be evaluated according to the study objectives.

Study Duration: Six-to-Sixty months

Participant Duration: Subject participation is intended to last for eight weeks after application of the dressings. Participant duration will begin upon obtaining informed consent and will end after eight weeks or earlier if the subject's wounds heal completely prior to eight weeks.

1.2 Schedule of Activities (SOA)

REQUIRED ASSESSMENTS & ACTIVITIES	Screening Visit Day 0	Initial Visit Day 1	Weekly visits (combined with dressing change visits) (Every 7 days ± 2 days)	Unscheduled Dressing change visits –	Final Visit (8 weeks from initial visit) ^{a,d}
Informed consent and screening form	X				
Wound assessment for eligibility	X				
Demographics and review of medical history		X			
List of medications taken by the subject		X	X	X	X
Application of new MPS-Ag or CMC-Ag dressings that will be compression wrapped ^b		X	X ^c	X ^c	
Pain assessment during removal and application of MPS-Ag dressing or CMC-Ag dressing, and dressing shrinkage evaluation		X ^{e,f}	X	X	X
Wound assessment (physical examination and infection evaluation)		X	X	X	X
Take wound photographs, record wound size and PUSAS score		X	X		X
Record analgesic use		X	X	X	X
Adverse event assessment		X-----X			

a: If the subject's wound heals prior to eight weeks, their participation in the study will be terminated. b: Dressings will be changed at least once weekly but can be changed earlier by the clinician depending on the level of exudate. c: MPS-Ag or CMC-Ag dressings will be removed, followed by application of a new MPS-Ag or CMC-Ag dressing, which will then be compression wrapped. d: Dressings will be removed, without application of a new MPS-Ag or CMC-Ag dressing, on the final day and all the assessments will be carried out. e: Pain assessment will be carried out only during application of MPS-Ag or CMC-Ag dressings on initial visit. f: Dressing shrinkage evaluation will not be carried out in the initial visit.
					

Comparison of marine polysaccharide and carboxymethylcellulose dressings

MED-2018-DIV71-026

30-JUN-2022

V 4.0

2. INTRODUCTION

2.1. Background & Rationale

Venous ulcers account for 80% of lower extremity ulcerations; they develop due to sustained venous hypertension, resulting from chronic venous insufficiency. There are various risk factors for venous ulceration such as varicose veins, deep vein thrombosis, poor calf muscle function, arterio-venous fistulae, obesity, and history of leg fracture. Recurrent venous ulceration has been known to occur in up to 70% of those at risk. Severe complications arising from venous ulcers include cellulitis, osteomyelitis, and sometimes malignant change. There are various treatment options for venous ulcers such as conservative management including use of compression bandages, mechanical treatment, use of medications, and surgical options.^{1,2,3}

There are numerous dressing types available that can be used to treat these ulcers. This study will compare a marine polysaccharide (MPS) dressing (Opticell[®] Ag⁺ dressing manufactured by Medline Industries, LP, henceforth referred to as “MPS-Ag dressing”) and a carboxymethylcellulose (CMC) dressing (Aquacel[®] Ag Advantage dressing manufactured by ConvaTec, henceforth referred to as “CMC-Ag dressing”), to determine which dressing better manages venous ulcers in subjects.

In this study, percentage reduction in wound size will be evaluated and compared between the two dressing types. Both the dressings will also be compared with regard to periwound skin condition, subject pain perception during dressing changes, and shrinkage of these dressings after their removal.

2.2. Clinical Products used in this study

2.2.1 Opticell[®] Ag⁺ dressing (MPS-Ag dressing)

The MPS-Ag dressing used in this study has gelling action which helps to remove dead, damaged, and infected tissues from the wound, by trapping and removing them later at dressing change. It is designed to provide intimate contact with the wound for gentle healing. It also contains ionic silver which provides broad spectrum antibacterial protection. This dressing is currently marketed in the United States and is indicated for partial- and full-thickness wounds of all drainage levels, first and second-degree burns, diabetic foot ulcers, venous stasis ulcers, arterial ulcers and leg ulcers of mixed etiology, pressure ulcers, and surgical wounds. The reference number of this product is MSC9845EP.⁴

2.2.2 Aquacel[®] Ag Advantage dressing (CMC-Ag dressing)

The CMC-Ag dressing used in this study incorporates two technologies, Hydrofiber[®] technology and Advantage technology, to help eliminate the key barriers to healing that are exudate, infection, and bioburden. It can be used on chronic and acute wounds that are infected or at risk of infection with varying exudate levels. This dressing is currently marketed in the United States. The reference number of this product is 422299.⁵

2.2.3 CoFlex[®] TLC Two Layer Compression Bandage System

The CoFlex[®] TLC Two Layer Compression Bandage System (henceforth, referred to as “compression bandage”) used in this study is used to manage venous disease. The first layer of dressing is soft foam which aims to wick away moisture. The second layer is composed of a short stretch of cohesive material that provides adaptive compression levels. It also comes with a nylon stocking that can be applied over the completed dressing for patient comfort and ease of movement under clothes and on bed sheets. The reference number of this product is AND7800.⁶

2.2.4 Skintegrity[®] wound cleanser

The Skintegrity[®] wound cleanser (henceforth, referred to as “wound cleanser”) used in this study is a non-cytotoxic wound cleanser, that does not hurt healthy cells, and does not delay wound healing process. It is specially formulated with a gentle surfactant to allow thorough and gentle cleansing of wounds of all stages. The reference number of this product is MSC6008.⁷

MPS-Ag, CMC-Ag, compression bandage, and wound cleanser used in this study will be provided to the site Principal Investigators (PI) by Medline Industries, LP.

2.3. Risk/Benefit Profile

2.3.1. Potential Study Risks

Subjects may experience an allergic reaction to MPS-Ag dressing, CMC-Ag dressing, compression bandage, wound cleanser, or skin protectant. Therefore, to mitigate this risk, subjects will be screened for known sensitivity to MPS-Ag, CMC-Ag, or compression bandage dressings, and other commonly used dressings, as well as other clinical products used in this study. Additionally, subjects will be under the care of a physician, who will be able to appropriately address any potential reaction from the dressings.

2.3.2. Potential Study Benefits

Through the use of these dressings, subjects may experience faster reduction in wound size, improved skin quality of the periwound tissue, and reduced pain during dressing changes.

2.3.3. Assessment of Potential Risk/Benefit Profile

The use of these currently marketed dressings presents minimal risk, while offering the potential for benefits to the subjects enrolled in the study. Therefore, the risk-benefit profile for the study is favorable.

3. OBJECTIVES AND ENDPOINTS

OBJECTIVES	ENDPOINTS	JUSTIFICATION FOR ENDPOINTS

Primary:
 
Evaluate and compare the change in wound size upon use of MPS-Ag dressing or CMC-Ag dressing.
	
Primary:
 
Changes in wound size.
	
Reduction in wound size is an indicator of wound healing.

Secondary:
 
1) Compare the periwound skin conditions after use of an MPS-Ag dressing or a CMC-Ag dressing. 2) Compare subject perception of pain during dressing changes. 3) Compare shrinkage of MPS-Ag and CMC-Ag dressings.
	
Secondary:
 
1) Peri ulcer skin assessment scale (PUSAS) score will be evaluated weekly for entire duration of study. 2) Subjective evaluation of subject pain perception during dressing changes using a numerical pain scale. 3) Evaluation of dressing shrinkage by measuring change in surface area of the dressings after their removal.
	
1) Periwound breakdown can delay healing, worsen wound progression, and may also cause pain. Therefore, in addition to assessing the wound bed, it is also important to assess the periwound and surrounding skin.⁸ 2) Evaluating subject pain perception during dressing change is also an indicator of ease of dressing change from the perspective of the subject. 3) Absorption of wound exudates decreases surface area of dressings. The ability of the dressing to absorb wound exudate, and yet maintain dressing size is an indicator of a high absorption capacity of the dressing.

4. STUDY DESIGN

4.1. Overall Design

This study is a multi-site, open-label randomized clinical trial comparing MPS-Ag dressing to CMC-Ag dressing and determining which dressing better manages these lower extremity venous ulcer wounds. Subjects will be randomized to receive either MPS-Ag dressing or the CMC-Ag dressing. The wound will be cleansed with the wound cleanser and designated dressing will be applied on the wound. It will then be wrapped with the compression bandage. The dressings will be changed at least once every week but can be changed earlier by the clinician depending on the level of exudate. There will be no home dressing changes. Wound assessments will be carried out weekly, such as change in wound size and PUSAS score evaluation. Subject pain perception during every dressing change will be recorded. If the clinician feels that peri-wound tissue requires protection, a skin protectant may be applied by the clinician or the clinical staff, per the facility's standard of care and clinician's discretion. Dressing shrinkage after removal of the dressings will also be determined. The Schedule of Activities in Section 1.2 describes the timing and sequencing of the events.

4.2. End of Study Definition

A subject's participation in the study may end at several critical points:

- Subject's wound heals, as determined by the site PI.
- Subject develops an infection at the wound site or any significant medical condition in the opinion of the site PI that precludes his/her continuation in the study.
- Subject has completed eight weeks of treatment.
- Subject withdraws from the study for any reason.

If the subject withdraws from the study, he or she will be replaced by another subject.

A clinical study report that has been approved by the Clinical Affairs Director will be issued following completion of the study.

5. STUDY POPULATION

5.1. Inclusion Criteria

A subject will be eligible to participate in the study if he or she satisfies *ALL* of the inclusion criteria below:

- Male or female, ≥ 18 years.
- Subject is able and willing to comply with requirements of this trial protocol.
- Subjects must be able to communicate effectively with study personnel.
- Subject has lower extremity venous ulcer wound, as determined by the site PI.

- Subject has adequate lower extremity arterial circulation as determined by the site PI at the time of enrollment
- Size of subject's wound is between 1cm² and 100cm².
- Duration of subject's wound is < 52 weeks.

5.2. Exclusion Criteria

A participant is ineligible for the study if he or she meets *ANY* of the criteria below:

- Subjects who are pregnant, nursing, or planning to become pregnant during the course of the study.
- Subjects who have known allergies to any ingredient(s) in the clinical products used in this study including silver.
- Subjects who do not wish to use product(s) derived from shellfish.
- Subjects with substance use disorder within the past six months.
- Subjects with active infection and/or currently receiving antibiotic treatment for the wound included in the study.
- Subjects who are currently enrolled in another research study which includes investigational treatment and/or medication.
- Subjects judged by the investigator or sub-investigator to be inappropriate as a subject of this study.
- Subject has previous or current systemic disease(s) which, in the judgement of the site PI, is likely to interfere with the study. However, subjects with well-controlled DM (HbA1c < 8.5) shall be permitted.
- Subjects who receive any additional product or procedure/activity that could influence wound healing, such as chemical debridement, use of other wound cleansers, additional hydrogel or alginate wound products etc.

5.3. Strategies for Recruitment and Retention

The site PI and/or sub-investigators and their staff regularly treat venous ulcer patients and will recruit eligible subjects from their practice. Each site will clearly and adequately convey that participation is voluntary, and that refusal to participate will not impact his or her medical treatment.

6. STUDY PROCEDURES AND ASSESSMENTS

6.1 Day 0 – Screening Visit and Informed Consent

6.1.1 Informed Consent

Prior to conducting study activities, written consent will be obtained from all participating subjects and documented on an informed consent form (ICF) that has been approved by an IRB/Ethics Committee. The ICF must be written in adherence to GCP and comply with all

elements required by FDA CFR 50.25 and ICH 4.8, state and local regulations, and additional elements relevant to specific study situations, (including a statement that Medline Industries, LP and authorities have access to subject records). A copy of the signed consent will be given to each participant.

6.1.2 Eligibility Screening

Potential participants will be screened for eligibility via a combination of the screening form and by a review of the potential participant's wound(s) and medical chart by the site PI and/or their staff.

If the participant has multiple wounds, the site PI will select the wound that meets the inclusion criteria. If more than one wound meets all the inclusion criteria, the site PI will choose the most clinically appropriate wound for the application of the dressings and will make a note of it in the Subject Screening form and the CRF.

6.2 Day 1 – Initial Visit

6.2.1 Demographics, Comorbidities, and Medication

Demographic information, subject co-morbidities, and a current medication list will be collected in order to understand if these variables affect the endpoints of wound size, periwound skin condition, and subject perception of pain during dressing changes. Information will be recorded on the CRFs.

6.2.2 Wound photograph and wound size measurement

During the initial visit, a member of the study staff will take photographs of the wound using a specialized wound camera with image analysis software (Insight® by eKare Inc.) and determine area and volume of the wound. The study staff will make every effort to obstruct identifiers such as tattoos/birth marks/scars in the wound images. In the event the camera or software malfunctions, manual measurement with a ruler will occur. Information will be recorded on the CRF.

6.2.3 Peri-ulcer skin assessment scale (PUSAS)⁹

Before application of the dressings, PUSAS will be used to measure the periwound skin condition. The instructions for use of assigning PUSAS score to the wounds will be provided. This score will be assigned to the wounds on which the dressings will be applied. Information will be recorded on the CRF.

6.2.4 Analgesic Usage

Since usage of analgesics will likely affect a subject's self-assessment of pain to dressing changes, analgesic usage will be recorded. This information will be recorded at the Initial Visit and all subsequent visits on the visit-specific CRFs.

After collecting all of the above information and data, the site PI or the qualified study staff will cleanse the wound, apply the designated dressing on the wound per the randomization schedule (see Section 8.2), and wrap it with compression bandage.

6.3 Dressing change visits - weekly and unscheduled

Subjects will have dressings removed at least once weekly (except on the initial visit) followed by application of new dressings. This will continue for eight weeks, from the initial visit, unless participation of the subject is terminated earlier as in section 4.2. The dressing change form will be completed at the initial visit and other subsequent dressing change visits. Additional information such as current analgesic, any new medication, irritation around the wound bed, and any abnormality in the wound status will be captured. If the clinician feels that the peri-wound tissue requires protection, a skin protectant may be applied by the clinician or the clinical staff, per the facility's standard of care and clinician's discretion, and will be recorded. The following information will also be recorded on the dressing change form:

6.3.1 Subject's perception of pain

A Numerical Rating Scale (NRS) will be used to measure perceived level of pain intensity on a numeric scale of 0-10, with 0 representing "no pain at all", and 10 representing "the worst pain ever possible".¹⁰ Subjects will be asked to rate their current level of pain to dressing changes, such as removal of the dressing (except in the initial visit) and application of new dressing, at the wound site using this verbal pain NRS.

6.3.2 Infection evaluation

During dressing change visits, the wound site included in the study will be evaluated for development of any infection. In the event of a suspected infection, clinical staff will collect a wound culture. Should a subject develop an infection as confirmed by wound culture, this will be noted as an adverse event (AE) and his or her participation in the study will be terminated. Subject participation will also be terminated if they receive any antibiotic, prophylactic or therapeutic, for treatment of the wound site included in the study.

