7 ADVERSE EVENTS

7.1 Definition of Adverse Event

In this study, an adverse event (AE) is any untoward medical occurrence related to the wound or treatment of the wound, including infection or a significant increase in pain during dressing changes.

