8.4 Data Analysis

Descriptive statistics will be provided for the key endpoints, including measures of central tendency (mean or median, as appropriate), measures of variation (standard deviations, coefficients of variation) and 95% confidence intervals and interquartile ranges, as appropriate. Specifically, these measures will be calculated for:

- Changes in wound size
- Average percent periwound global score reduction
- Subject's pain rating during dressing changes
- Dressing shrinkage determined upon removal of dressings
- Proportion of subjects who develop an infection

The key assessment for differences in dressing performance will be based on the comparison of mean reduction in wound size for each dressing type. The specific details of the statistical testing will be provided in a forthcoming SAP. Comparisons of reduction in PUSAS score, subject pain ratings, and dressing shrinkage will also be made between the two dressing types, with specific details described in the SAP.

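### Section 6.3.2 ties the infection AE to a positive culture, 7.1 and 4.2 do not, and 8.4 does not say which infections count, so treated but unconfirmed cases may be missed

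*Combined protocol and SAP*

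**What the plan says.** Section 6.3.2 is the working instruction for sites. It first requires a culture: "In the event of a suspected infection, clinical staff will collect a wound culture". It then says "Should a subject develop an infection as confirmed by wound culture, this will be noted as an adverse event (AE", and ends participation for that subject. A second exit follows: "Subject participation will also be terminated if they receive any antibiotic, prophylactic or therapeutic, for treatment of the wound site included in the study". No AE or infection coding is attached to the second exit, and prophylactic and therapeutic use are handled together.

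Section 7.1 defines an AE as "any untoward medical occurrence related to the wound or treatment of the wound, including infection or a significant increase in pain during dressing changes". There is no culture condition.

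Section 4.2 lists among the reasons for ending participation: "Subject develops an infection at the wound site or any significant medical condition in the opinion of the site PI". Again there is no culture condition. The wording leaves open whether the PI's opinion governs the infection or only the medical condition.

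Section 8.4 lists "Proportion of subjects who develop an infection" among its descriptive summaries. It gives no case definition and does not say whether the figure comes from AE records, culture results or exit reasons. It defers the details of its between-dressing comparisons to a forthcoming SAP, and infection is not one of the comparisons named there.

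Two further places bear on the count. Section 6.3 says of dressing-change visits that "any new medication, irritation around the wound bed, and any abnormality in the wound status will be captured". Section 8.3 restricts all analyses to subjects with valid wound size at the initial and final visits, and 6.4 defines the final visit as week 8 or healing.

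**The concern.** The sections do not agree on what makes a wound infection a recordable event, and the summary in 8.4 does not choose between them. Two sites could each follow the protocol and record the same patient differently: one enters an AE under 7.1, while the other sees a negative culture under 6.3.2, ends participation because an antibiotic was started, and enters no infection.

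Infection is the one adverse event that 8.4 names for summary (pain ratings are also listed, and a significant increase in pain is an AE under 7.1). Section 7.5 lists infection as an expected event, and 2.2 describes both products as antimicrobial or intended for wounds at risk of infection. Under-recording would therefore affect the main safety statement of the report. The trial is open-label (4.1), so the decision to treat on suspicion is made with the arm known. Any under-recording need not be equal in the two arms.

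**Working it through.** **Step 1. The cases, set against each rule.**

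| Case | 6.3.2 | 7.1 | 8.4 |
|---|---|---|---|
| Culture positive, with or without antibiotic | AE, exit | AE | Counted on any reading |
| Antibiotic started while culture is pending, result later positive | Exit by antibiotic; the result meets the AE rule | AE | Should count, but how a result arriving after exit is entered is not stated |
| Infection diagnosed, culture negative or unusable, therapeutic antibiotic | Exit; no AE instruction | AE | Undefined |
| Culture never taken | Departs from the culture requirement | AE if infection is diagnosed | Undefined |
| Prophylactic antibiotic, no infection | Exit | Not an infection | Should not count, but nothing separates it from therapeutic use |

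The gap lies in the third row. The fourth is a protocol deviation, not a fault in the definition. The fifth shows why antibiotic exits cannot simply be relabelled as infections.

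**Step 2. Inputs.** The documents state no infection rate, no share of infections confirmed by culture and no rate of antibiotic use, so there is no infection figure in the plan to reproduce. The only usable figures are the totals in 8.1: 68 required and a target of 80. The 68 reproduces. The effect is d = (40 − 33)/10 = 0.7, and a two-sided t-test at 0.05 with 80% power needs 33.02 per arm, rounded up to 34, or 68 in total (power 81.2%). It serves here only as a denominator.

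**Step 3. Effect of the case definition (all rates assumed).** Reported proportion = k(1 − m)/N, where k is the number of infections diagnosed clinically and m is the share without culture confirmation and left uncounted.

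- N = 80, k = 8: m = 0 gives 8/80 = 10.0%; m = 0.25 gives 6/80 = 7.5%; m = 0.5 gives 4/80 = 5.0%.
- N = 80, k = 4 to 12, m = 0 to 0.5: a clinical proportion of 5.0% to 15.0% is reported as between 2.5% and 15.0%.
- N = 68, k = 4 to 12, same m: 5.9% to 17.6% is reported as between 2.9% and 17.6%.

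**Step 4. Unequal recording between arms (assumed).** With 40 per arm and 20% diagnosed, each arm has 8 infections. If 90% are confirmed in one arm and 50% in the other, the reported figures are 0.20 × 0.9 = 18% and 0.20 × 0.5 = 10%. The split is chosen to show sensitivity and is not a forecast.

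**Step 5. The analysis population acts separately.** A subject ended for infection may have no final-visit measurement as 6.4 defines it. If half of 8 infected subjects among 80 drop out of the evaluable set, the proportion is 4/(80 − 4) = 4/76 = 5.3% instead of 10.0%, even if every infection is culture-confirmed. Analysing everyone would not repair Step 3, and a better definition would not repair this.

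**The case against.** The strongest reply is that the AE definition already covers these subjects. Section 6.3.2 says what happens when a culture confirms infection; it does not say that an unconfirmed infection is not an AE, and 7.1 includes infection without qualification. A reader might infer that the protocol records infections only on culture, that subjects removed for treated infection do go uncounted, and that the proportion is too low. The documents do not support any of these as fact. The restriction is an inference from 6.3.2, 8.4 does not say it counts culture-confirmed AEs alone, and the undercount could be nil.

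Other parts of the reply also stand. Every suspected infection is to be cultured, and a pending culture that turns positive still meets 6.3.2. Section 4.2 governs exit, not AE recording. New medication and abnormal wound status are captured, so some cases may be recoverable, and the CRFs are not part of the documents, so they may already hold the reason for an antibiotic. Infection is summarised descriptively, so the plan rests no formal comparison of the dressings on it. A negative culture may also mean there was no infection, and culture is the more objective criterion in an open-label trial.

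What this does not answer is the disagreement itself. A culture qualifier in the section that staff will use invites them to treat it as the criterion. Recoverable data are not a counting rule, and nothing in the protocol requires therapeutic and prophylactic use to be told apart.

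**Conclusion.** The concern holds as an inconsistency with a possible undercount. Sections 6.3.2 and 7.1 are not aligned on when an infection is recorded, the antibiotic exit carries no infection coding, and 8.4 does not define its numerator. Subjects removed for a clinically treated infection with a negative or unusable culture may go uncounted, and the infection proportion may be too low.

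The documents do not allow the size to be estimated. The illustrations run from no undercount to half of clinically diagnosed infections, and they rest wholly on assumed rates. They also treat each clinically diagnosed case as an infection, which is the point in dispute. A reader might go further and infer that one dressing will be made to look safer. The open-label design makes unequal recording possible, but nothing in the documents shows that it will occur or in which direction.

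**What to change.** Reconcile 4.2, 6.3.2, 7.1 and 8.4 for recording and counting only, with no change to care or to the exit rules:

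- Record as an AE every study-wound infection diagnosed by the site PI, whatever the culture result.
- Record each antibiotic given for the study wound as prophylactic or therapeutic.
- In 8.4, report by arm (a) culture-confirmed infections and (b) all infections diagnosed by the site PI or therapeutic antibiotic starts for the study wound.
- Use all randomised subjects as the denominator for both counts, not only the evaluable population of 8.3. Otherwise subjects ended for infection may still drop out.

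The cost is wording in four sections, an exception to 8.3 for this summary, and one CRF field if it is not already there. Medications are already collected at each visit. The change should be made before analysis, because the intent behind an antibiotic may be hard to reconstruct later. The downside is that count (b) may include culture-negative cases that are not infections; showing (a) beside it makes that visible and avoids having to settle on a single definition.
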